### Power for Analysis of Selected Key Secondary Efficacy Endpoint

A key secondary efficacy endpoint is the absolute change in SwCl from baseline through Week 24. Assuming a within-group SD of 14 mmol/L and a 10% dropout rate at Week 24, a sample size of 200 subjects in each treatment group will have more than 90% power to detect a difference between the treatment groups of -5 mmol/L for the absolute change in SwCl from baseline through Week 24, based on a 2-sided, 2-sample *t*-test at a significance level of 0.05.

## 12.2 Analysis Sets

The following analysis sets are defined: All Subjects Set, Full Analysis Set (FAS), Safety Set, and Per-protocol Set (PPS).

The **All Subjects Set** will include all subjects who were randomized or received at least 1 dose of study drug. This analysis set will be used for all individual subject data listings and disposition summary tables, unless otherwise specified.

The **FAS** will include all randomized subjects who carry the intended *CFTR* allele mutation(s) and received at least 1 dose of study drug during the Treatment Period. The FAS will be used to summarize subject demographics and baseline characteristics, and for analyses of all efficacy endpoints in which subjects will be analyzed according to their randomized treatment group, unless otherwise specified.

The **Safety Set for the Run-in Period** will include all subjects who received at least 1 dose of study drug in the Run-in Period. This safety set will be used only for individual subject data listings, unless otherwise specified.

The **Safety Set for the Treatment Period** will include all subjects who received at least 1 dose of study drug during the Treatment Period. The Safety Set will be used for all safety analyses in

which subjects will be analyzed according to the treatment they actually received, unless otherwise specified.

The PPS will be a subset of FAS after excluding subjects with certain important protocol deviations and other situations; details will be provided in the statistical analysis plan (SAP).

### **12.3 Statistical Analysis**

This section presents a summary of the planned analyses for this protocol. Statistical analysis details will be provided in the SAP, which will be finalized before the clinical data lock for the study.

#### **12.3.1 General Considerations**

**Continuous variables** will be summarized using the following descriptive summary statistics: number of subjects (n), mean, SD, median, minimum value (min), and maximum value (max).

**Categorical variables** will be summarized using counts and percentages.

**Baseline** unless otherwise specified, will be defined as the most recent non-missing measurement (scheduled or unscheduled) collected before the first dose of study drug in the Treatment Period (i.e., the Day 1 Visit). For SwCl, baseline will be defined as the average of the Day -14 and Day 1 values. If either the Day -14 or the Day 1 value are missing, the other will be used as the average.

**Absolute change** from baseline will be calculated as post-baseline value – baseline value.

The **Treatment-emergent (TE) Period for the Run-in Period** will be from the first dose date of study drug in the Run-in Period to (1) the first dose date of study drug in the Treatment Period for subjects who complete the Run-in Period and continue to the Treatment Period, or (2) 28 days after the last dose date of study drug in the Run-in Period or to the completion of study participation date (as defined in Section 9.1.7), whichever occurs first, for subjects who do not continue to the Treatment Period (e.g., subjects who do not meet the conditions to enter the Treatment Period).

The **TE Period for the Treatment Period** will include the time from the first dose date of study drug in the Treatment Period to 28 days after the last dose of the study drug or to the completion of study participation date, whichever occurs first.

#### **12.3.2 Background Characteristics**

Subject disposition, demographic and baseline characteristics, prior and concomitant medications, exposure, compliance, and important protocol deviations will be summarized. Details of the analysis will be provided in the SAP.

#### **12.3.3 Efficacy Analysis**

All efficacy analyses described in this section will be based on the FAS, unless otherwise specified. Only the principal features of the efficacy analysis will be presented in this section. Additional details will be included in the SAP.

##### **12.3.3.1 Analysis of Primary Endpoint**

The primary efficacy endpoint is the absolute change from baseline in ppFEV1 through Week 24 (estimated by averaging Weeks 16 and 24). The primary analysis will be conducted with clinic spirometry data only and will be performed using a mixed-effects model for repeated measures

(MMRM) with absolute change from baseline in ppFEV1 at Day 15, Week 4, Week 8, Week 16, and Week 24 as the dependent variable. The model will include treatment group, visit, and treatment-by-visit interaction as fixed effects, with continuous baseline ppFEV1, continuous baseline SwCl, and age at screening (<18 versus ≥18 years of age) as covariates. The model will be estimated using restricted maximum likelihood. Denominator degrees of freedom for the F test for fixed effects will be estimated using the Kenward-Roger approximation. An unstructured covariance structure will be used to model the within-subject errors. If the model estimation does not converge, a compound symmetry covariance structure will be used instead. Conditional on the observed data and covariates, missing data will be assumed to be missing at random; therefore, no imputation of missing data will be performed.

The primary result obtained from the model will be the estimated treatment difference through Week 24. The adjusted mean with a 2-sided 95% CI will be provided. The primary null hypothesis will be rejected and non-inferiority demonstrated if the lower bound of the 95% CI is ≥-3.0. The estimated within group change from baseline and the treatment difference at each post-baseline visit will also be provided, obtained from the model.

The primary null hypothesis of non-inferiority described above will be tested based on the FAS. If the lower bound of the 95% CI is greater than 0, then superiority for the primary endpoint is demonstrated and the 2-sided *P* value for superiority will be calculated.

Sensitivity analyses for handling missing data will be described in the SAP.

Supportive analyses and subgroup analyses (as appropriate) will also be described in the SAP.

### **12.3.3.2 Analysis of Secondary Endpoints**

#### **Analysis of Key Secondary Variables**

- Absolute change from baseline in SwCl through Week 24: The analysis of this variable will be based on an MMRM similar to the analysis of the primary endpoint above, with absolute change from baseline in SwCl at Day 15, Week 4, Week 16, and Week 24 as the dependent variable. The primary result obtained from the model will be the estimated treatment difference through Week 24. The LS mean estimate with a 2-sided 95% CI and a 2-sided *P* value will be provided. The estimated within group change from baseline and the treatment difference at each post-baseline visit, obtained from the model, will also be provided.
- Proportion of subjects with SwCl <60 mmol/L through Week 24 (pooled with data from Study VX20-121-103): The response corresponding to SwCl <60 mmol/L through Week 24 based on pooling data from FAS of this study and from Study VX20-121-103 (which has a similar study design and will evaluate CF subjects with other genotypes) will be analyzed. Details of this analysis will be described in the SAP.
- Proportion of subjects with SwCl <30 mmol/L through Week 24 (pooled with data from Study VX20-121-103): The response corresponding to SwCl <30 mmol/L through Week 24 based on data pooled from the FAS of this study and from Study VX20-121-103 will be analyzed. Details of this analysis will be specified in the SAP.

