## **6 STUDY OBJECTIVES**

### **6.1 Primary Objective**

To evaluate the efficacy of VX-121/TEZ/D-IVA in CF subjects who are heterozygous for *F508del* and a minimal function mutation (F/MF subjects)

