### Power for Primary Analysis of Primary Efficacy Endpoint

The primary efficacy endpoint is the absolute change from baseline in ppFEV1 through Week 24. The primary null hypothesis to be tested is that the mean absolute change in ppFEV1 from baseline through Week 24 for VX-121/TEZ/D-IVA is inferior by >3 percentage points compared to ELX/TEZ/IVA.

The non-inferiority margin represents a clinically acceptable loss of effectiveness as outlined in regulatory guidances. Furthermore, a statistical approach using the Rothmann method recommends that the non-inferiority margin preserve at least 50% of the treatment effect of the active control (ELX/TEZ/IVA) compared to placebo, where the treatment effect is estimated by the lower bound of the 95% CI. In the overall population eligible for this study, the lower bound of the 95% CI of the treatment effect is approximately 12 percentage points for ppFEV1. The selected non-inferiority margin of 3 percentage points is consistent with this statistical method and the non-inferiority margin for ppFEV1 used in clinical studies evaluating symptomatic CF treatments.

The null hypothesis will be tested at a 1-sided significance level of 0.025.

Assuming a within-group SD of 8 and 10% drop-out rate at Week 24 and a treatment difference of 0 between VX-121/TEZ/D-IVA and ELX/TEZ/IVA, a sample size of 200 subjects in each group for a total of 400 subjects will have more than 90% power to test the primary hypothesis for the primary endpoint, based on a 1-sided, 2-sample *t*-test at a significance level of 0.025.

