### **12.3.3.3 Multiplicity Adjustment**

A hierarchical testing procedure will be used to control the overall type I error at an alpha of 0.05. The key secondary endpoints will be formally tested at an alpha of 0.05 only if the primary analysis of absolute change from baseline in ppFEV1 through Week 24 is statistically significant, i.e., null hypothesis of inferiority has been rejected. For a test at any step to be considered statistically significant within the testing hierarchy, it must be statistically significant, and all previous tests (if any) within the hierarchy must be statistically significant at the 0.05 level 2-sided (1-sided 0.025 level for the primary endpoint). Additional details will be provided in the SAP.

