8.3.2 Analysis of Key Secondary Efficacy Variables

The tests for absolute change from baseline in SwCl through Week 24 (continuous variable) based on the FAS and the proportion of subjects with SwCl <60 mmol/L and SwCl <30 mmol/L through Week 24 based on the PFAS will be subject to multiplicity control. Note that the within-study analyses of the proportion of subjects with SwCl <60 mmol/L through Week 24 and the proportion of subjects with SwCl <30 mmol/L through Week 24 based on the FAS are Other Secondary Endpoints and are not subject to multiplicity control; analyses of these endpoints are described in 8.3.3.

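### Free improvement: the only error-controlled SwCl <60 and <30 mmol/L tests are pooled with Study 103, and the already planned F/MF-only versions could be added last in the sequence at no alpha cost

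*Protocol*

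**What the plan says.** The primary objective (Protocol 6.1) is "To evaluate the efficacy of VX-121/TEZ/D-IVA in CF subjects who are heterozygous for" *F508del* and a minimal function mutation.

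On multiplicity, Protocol 12.3.3.3 states: "A hierarchical testing procedure will be used to control the overall type I error at an alpha of 0.05". It admits only the key secondary endpoints to formal testing after the primary test. SAP 8.3.2.3 fixes the order:

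1. ppFEV1 non-inferiority, F/MF only (Full Analysis Set, FAS)
2. Mean SwCl change through Week 24, F/MF only (FAS)
3. SwCl <60 mmol/L through Week 24, pooled with Study 103
4. SwCl <30 mmol/L through Week 24, pooled with Study 103

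The list ends there. Tests 3 and 4 are obtained by "pooling data from FAS of this study and from Study VX20-121-103 (which has a similar study design and will evaluate CF subjects with other genotypes" (Protocol 12.3.3.2). The reason given for pooling is power (SAP 8.3).

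The pooled GEE model (SAP 8.3.2.2) has genotype group (F/MF, F/F, F/G, F/RF, TCR/non-F) as a main effect and lists no treatment-by-genotype term. If the model does not converge, genotype may be collapsed to three levels or removed. The summary is one odds ratio.

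The same two endpoints within Study 102 have their own GEE models on the FAS (SAP 8.3.3.2). According to SAP 8.3.2 they "are Other Secondary Endpoints and are not subject to multiplicity control". SAP 8.1 and 8.3 accordingly make their P values nominal.

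**The concern.** The two threshold endpoints are important enough to be key secondary, yet the trial tests them under error control only in a population wider than the one in its objective. A significant pooled odds ratio shows an effect in the mixture. It does not reject the null hypothesis for F/MF subjects.

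If all four planned tests succeed, the evidence on <60 and <30 in F/MF subjects is still nominal. A fixed sequence can carry further tests at its end without charge, and these two analyses are already written, so that limitation is avoidable. What is at stake is the status of two threshold conclusions in the trial's own population. The validity of the tests already in the sequence is not in question.

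**Working it through.** **1. The plan's own power figures.** Inputs from Protocol 12.1: "Assuming a within-group SD of 8 and 10% drop-out rate at Week 24 and a treatment difference of 0"; the null is that the new regimen "is inferior by >3 percentage points compared to ELX/TEZ/IVA"; "The null hypothesis will be tested at a 1-sided significance level of 0.025"; and "a sample size of 200 subjects in each group for a total of 400 subjects will have more than 90% power". Evaluable per arm: 200 × 0.9 = 180. Normal approximation: power = Φ(Δ / (SD·√(2/n)) − 1.96).

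- ppFEV1: 3 / (8·√(2/180)) = 3 / 0.843 = 3.558, so power = Φ(1.598) = 0.945.
- Mean SwCl change (SD 14, difference 5, 2-sided 0.05): 5 / (14·√(2/180)) = 5 / 1.476 = 3.388, so power = Φ(1.428) = 0.923.

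Both agree with the stated figure of more than 90%. The documents give no power for any responder endpoint.

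**2. Alpha cost of adding the F/MF-only tests as tests 5 and 6.** In a fixed sequence, the first true null in the order must be rejected before any other true null can be tested. The family-wise error is therefore at most the level of that one test, whatever the number of later steps or the correlations. A simulation of 400,000 replicates (assumed correlations 0.6 among SwCl tests and 0.3 with ppFEV1) agrees:

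| Nulls that are true | 4 tests | 6 tests |
|---|---|---|
| All | 0.025 | 0.025 |
| Pooled and F/MF-only responder | 0.049–0.050 | 0.049–0.050 |
| F/MF-only responder | 0 | 0.050 |

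Tests 1 to 4 are carried out before the added ones, so their alpha, order and power cannot change. By comparison, if a reader treats the two nominal P values as significant at 0.05 with both nulls true, the chance of at least one false claim is 0.087–0.088 at correlation 0.6, or 1 − 0.95² = 0.0975 if the tests are independent.

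**3. How far Study 103 could carry a pooled claim.** The documents give neither responder rates nor the size of Study 103, so these inputs are assumed. Take no F/MF responder effect (25% in both arms, 180 per arm) and 30% v 40% in Study 103 with 180 per arm, weighting each study by size.

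- Weighted difference = 0.5 × 0 + 0.5 × 0.10 = 0.05.
- SE = √(0.25 × (0.375 + 0.45)/180) = 0.0339.
- Probability of significance = Φ(0.05/0.0339 − 1.96) = 0.31.

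For 30% v 45% it is 0.60. With 250 per arm in Study 103 the two values are 0.46 and 0.79.

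These figures ignore the gate. The pooled tests are formal only after test 2, which is F/MF only. If there is no mean SwCl effect in F/MF subjects, test 2 succeeds in the favourable direction with probability 0.025. A formal pooled claim preceded by a favourable test 2 then has probability at most 0.025. The 0.31–0.79 values are upper bounds for a different case: a real mean shift in F/MF subjects with no change in the proportion below the threshold.

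**4. Power of the added tests.** Two-proportion test, 180 per arm, 2-sided 0.05, pooled variance under the null; rates assumed.

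- 25% v 35%: null SE = √(2 × 0.30 × 0.70/180) = 0.0483; alternative SE = √((0.1875 + 0.2275)/180) = 0.0480; power = Φ((0.10 − 1.96 × 0.0483)/0.0480) = 0.54.
- 20% v 35%: null SE = √(2 × 0.275 × 0.725/180) = 0.0471; alternative SE = √((0.16 + 0.2275)/180) = 0.0464; power = Φ((0.15 − 1.96 × 0.0471)/0.0464) = 0.89.

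These are ceilings, because tests 1 to 4 must all succeed first. At the planning values, tests 1 and 2 both succeed with probability 0.945 × 0.923 = 0.87 if independent. No figure can be given for tests 3 and 4.

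**The case against.** The plan is open about what it does. It names the pooled population in the estimand, gives power as its reason, adjusts for genotype and specifies the F/MF-only models, so a reader can check consistency. The objective asks for efficacy in F/MF subjects, and two controlled F/MF-only tests, ppFEV1 and mean SwCl change, already address it. No stated objective requires a responder claim. The argument that a last place costs no alpha would apply equally to exacerbations or CFQ-R. The edit also reaches statements in both documents.

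All of this stands, and it limits the weight of the point. It does not explain why analyses already planned, on endpoints the sponsor itself made key secondary in pooled form, stay outside a sequence that could carry them. The power rationale justifies testing the pooled versions first, and the proposal keeps them first. The reason to choose these two over other secondary endpoints is that they restate the last two controlled tests in the trial's own population.

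A reader might go further and infer that the pooled claim can be carried wholly by Study 103. The documents do not support that as a likely outcome, because the F/MF-only mean SwCl test comes first. It would take a mean shift in F/MF subjects without a threshold effect, which is possible but which nothing in the documents suggests.

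**Conclusion.** The point holds as an improvement. A pooled rejection does not by itself establish an effect on SwCl <60 or <30 in F/MF subjects, and the F/MF-only analyses as planned give only nominal inference. Adding them last converts that to controlled inference with family-wise error still at 0.05 and no effect on the four existing tests. This result follows from the structure of a fixed sequence and needs no assumption about rates.

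The benefit is less certain. Under assumed rates, each added test has power of about 0.54 for a 10-point difference and 0.89 for a 15-point difference, less the chance of failing earlier.

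Two stronger readings are not supported. The plan as written does not inflate type I error, since it declares these P values nominal. Nor does it leave F/MF subjects without a controlled sweat chloride conclusion, since mean SwCl change is tested in them. The documents do not say how Study 103 uses the pooled endpoints in its own testing, so nothing is concluded about that.

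**What to change.** Before database lock and unblinding, keep the present order in SAP 8.3.2.3 and append, after the pooled <30 test:

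- (a) proportion with SwCl <60 mmol/L through Week 24 within Study 102 (FAS); then
- (b) proportion with SwCl <30 mmol/L through Week 24 within Study 102 (FAS).

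Test each at 2-sided 0.05 only if all earlier steps are significant, using the GEE models already in SAP 8.3.3.2.

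Align the statements that now exclude these tests: the multiplicity paragraph in SAP 8.1, the text on nominal P values in SAP 8.3, the exclusion in SAP 8.3.2, and Protocol 12.3.3.3, which limits formal testing to the key secondary endpoints. If the protocol is not reissued, record the change in SAP 2.1, which currently lists none. The endpoints can stay in the other-secondary lists if the text says that these two are also tested in the sequence. SAP section 3 provides for documented amendments before lock.

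The cost is a short SAP amendment and the matching protocol statement. It needs no new data, models or subjects, and takes no alpha or power from the existing tests.

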#### **Analysis of Other Secondary Variables**

The other secondary variables include: number of PEx through Week 52, absolute change from baseline in CFQ-R RD score through Week 24, absolute change from baseline in ppFEV1

through Week 52, absolute change from baseline in SwCl through Week 52, proportion of subjects with SwCl <60 mmol/L through Week 24, and proportion of subjects with SwCl <30 mmol/L through Week 24. The analysis details for these variables will be described in the SAP.

### **12.3.3.3 Multiplicity Adjustment**

A hierarchical testing procedure will be used to control the overall type I error at an alpha of 0.05. The key secondary endpoints will be formally tested at an alpha of 0.05 only if the primary analysis of absolute change from baseline in ppFEV1 through Week 24 is statistically significant, i.e., null hypothesis of inferiority has been rejected. For a test at any step to be considered statistically significant within the testing hierarchy, it must be statistically significant, and all previous tests (if any) within the hierarchy must be statistically significant at the 0.05 level 2-sided (1-sided 0.025 level for the primary endpoint). Additional details will be provided in the SAP.

### **12.3.3.4 Analysis of Other Endpoints**

The analysis details of other endpoints will be described in the SAP.

## **12.3.4 Safety Analysis**

All safety analyses will be based on the data from the TE period for the Treatment Period for all subjects in the corresponding Safety Set for the Treatment Period, unless otherwise specified.

The overall safety profile of study drug will be assessed in terms of the following safety and tolerability assessments:

- Treatment-emergent adverse events (TEAEs)
- Clinical laboratory values (i.e., hematology, serum chemistry, coagulation, and urinalysis as applicable)
- Standard 12-lead ECGs
- Vital signs
- Pulse oximetry
- Ophthalmological examinations

Only descriptive analysis of safety will be performed and no statistical testing will be performed. The safety data during the Run-in Period will only be presented in listings, unless otherwise specified. Additional details will be provided in the SAP.

LFT elevations, creatine kinase elevations, rash, cataracts, hypoglycemia, and neuropsychiatric events will be designated as AEs of special interest.

## **12.4 Interim Analysis**

No interim analysis will be performed.

## **12.5 Data Monitoring Committee Analysis**

The DMC (Section 9.1.9) will conduct safety reviews of study data as outlined in the DMC Charter.

## **12.6 Clinical Pharmacology Analysis**

### **12.6.1 Pharmacokinetic Analysis**

The PK analysis of VX-121, TEZ, and D-IVA may be performed using nonlinear mixed-effects modeling and/or standard noncompartmental analysis, as data allow. Metabolites, including M1-TEZ, may be included in the analyses as supported by data. Descriptive statistics will be used to summarize PK parameter values for all analytes.

A detailed description of the planned PK analysis will be presented in the clinical pharmacology analysis plan (CPAP).

### **12.6.2 Pharmacokinetic/Pharmacodynamic Analyses**

PD assessments to be included in PK/PD analyses may include SwCl, ppFEV1, as well as other endpoints such as CFQ-R RD score.

A sequential approach will be used to perform the population PK/PD analysis. The Bayesian estimates of individual PK parameters from the final population PK model will be used to simulate PK profiles for each subject. The simulated VX-121, TEZ, D-IVA, or metabolite plasma concentrations will be used in the potential pharmacological response models to describe changes in each endpoint from baseline. Fixed- and random-effect parameter estimates and the associated asymptotic SEs will be estimated.

